#### 3. STUDY DESIGN

#### 3.1 Overall Design

This is a multicenter, open-label, single-arm, Phase 2 clinical study to assess the efficacy and safety of quizartinib monotherapy in patients with FLT3-ITD positive AML who have relapsed or are found to be refractory within 6 months after initial remission induction therapy (it is not taken into consideration whether they have received HSCT or not).

Quizartinib will be administered at an initial dose of 30 mg/day. For patients receiving strong CYP3A4 inhibitors, an initial dose of 20 mg/day will be used. Quizartinib will be orally administered once daily every morning. Treatment with quizartinib will be administered in 28-day cycles and continued until "5.7.1 Discontinuation Criteria for Treatment with the Study Drug" are met.

Whether to increase or maintain the dose of quizartinib will be determined on Day 16 of Cycle 1 and Day 1 of Cycle 2 in accordance with "5.2.4.3 Criteria for Dose Increase of the Study Drug." A 12-lead ECG will be measured at least once weekly for the first 2 weeks after a dose increase to carefully confirm the presence or absence of QTcF prolongation after the dose increase. When doing this, triplicate ECG recordings will be obtained.

This study will be conducted using a two-stage design. In Stage 1, interim analysis will be performed when 25 patients have been included in the efficacy analysis set. As a result, the study will be terminated both if CR, CRp, or CRi (CRc) is achieved in 3 or fewer patients (the treatment will be determined to be ineffective), or if CR, CRp, or CRi (CRc) is achieved in 11 or more patients (the treatment will be determined to be effective). Meanwhile, if CRc is achieved in 4 to 10 patients, registration of patients will be continued until 41 patients are included in the efficacy analysis set (addition of 16 patients in Stage 2). When the study proceeds to Stage 2, the results of the final analysis

will be assessed as follows: Concerning the 41 patients included in the efficacy analysis set, if CRc is achieved in 15 or more patients, the treatment is determined to be effective (rejection of the null hypothesis). The details of interim analyses are shown in "11.4 Interim Analysis."

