### Assessment criteria for dose increase on Day 1 of Cycle 2 or later

For patients who have not achieved CR, CRp, or CRi after at least 1 cycle of treatment with quizartinib\* and whose condition before the decision on dose increase satisfies the following requirements, the dose of quizartinib will be increased.

- Absence of Grade 3 or more severe treatment-related non-hematological toxicity
- 60 ms or shorter increase in QTcF interval from baseline
- Absence of hypoplastic bone marrow upon the decision of a dose increase
- \* At least 1 cycle of treatment with quizartinib: Treatment with quizartinib is given for at least 13 consecutive days

For patients who have relapsed after achieving CR, CRp, CRi, or PR, and satisfy the assessment criteria for dose increase on Day 1 of Cycle 2 or later, the dose of quizartinib may be increased. The dose will be increased to 60 mg/day if strong CYP3A4 inhibitors are not concomitantly used, and to 30 mg/day if strong CYP3A4 inhibitors are concomitantly used.

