## 5.4 Dose Interruptions and Reductions

If any of the criteria in Section 5.4.1 to Section 5.4.4 apply, treatment with quizartinib will be interrupted or the dose of quizartinib will be reduced. The dose of quizartinib will be reduced by one level at a time according to Table 5.4-1. If quizartinib is administered at a dose of 20 mg/day, a further dose reduction is not allowed.

Table 5.4-1 Method of Dose Reduction of Quizartinib

Dose	One level Reduced Dose
60 mg/day	30 mg/day
30 mg/day	20 mg/day
20 mg/day	No dose reduction

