## **5.4.1 QTcF Prolongation**

In case of QTcF prolongation, the dose will be reduced in the following manner.

Table 5.4-2 Criteria for Dose Interruption and Reduction When QTcF Prolongation Occurs during Treatment with Quizartinib at 30 mg/day or 60 mg/day

CTCAE Grade	Method of Dose Reduction		
Grade 2	
 
Reduce the dose by one level. It is not necessary to interrupt treatment.
 
The dose may be increased to the dose before dose reduction if QTcF prolongation recovers to Grade 1 or less severe after treatment at the reduced dose for at least 28 days.
 
		
Grade 3	
 
Interrupt quizartinib treatment for a maximum of 14 days.
 
Resume quizartinib treatment at a one level reduced dose, relative to the dose immediately before the interruption, if the increase in QTcF interval from baseline is 30 ms or shorter or the QTcF interval recovers to 450 ms or shorter within 14 days after the onset.
 
Do not increase the dose after resumption of quizartinib treatment.
 
		
Grade 4	Discontinue quizartinib treatment.		

For the treatment of QTcF prolongation, "9.10.2 Measures Taken in Case of QTcF Prolongation" should be followed.

Table 5.4-3 Criteria for Dose Interruption and Reduction When QTcF Prolongation Occurs during Treatment with Quizartinib at 20 mg/day

CTCAE Grade	Method of Dose Reduction	
Grade 2	
 
Interrupt quizartinib treatment for a maximum of 14 days.
 
Resume quizartinib treatment at a dose of 20 mg/day if QTcF prolongation recovers to Grade 1 or less severe.
 
	
Grade 3	
 
[If strong CYP3A4 inhibitors are concomitantly used]
 
Interrupt quizartinib treatment for a maximum of 14 days.
 
Resume quizartinib treatment at a dose of 20 mg/day if the increase in QTcF interval from baseline is 30 ms or shorter or the QTcF interval recovers to 450 ms or shorter within 14 days after the onset, and the concomitant use of strong CYP3A4 inhibitors is discontinued.
 
Do not increase the dose after resumption of quizartinib treatment.
 
[If strong CYP3A4 inhibitors are not concomitantly used]
 
Discontinue quizartinib treatment.
 
	
Grade 4	Discontinue quizartinib treatment.	

For the treatment of QTcF prolongation, "9.10.2 Measures Taken in Case of QTcF Prolongation" should be followed.

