#### 9.10 Electrocardiograms

#### 9.10.1 Measurement Method

ECG will be performed consecutively three times (triplicate ECGs) at intervals of 3 to 5 minutes after patients have remained at rest in the supine position for 10 minutes. The QTcF interval will be determined as the average of three measurements and used for safety evaluation and for making a decision on quizartinib dose increase on Day 16 of Cycle 1 and on Day 1 of Cycle 2 or later. The ECG results will be transferred to the Central ECG Reading Center (eResearch Technology, Inc. [ERT]). The investigators may check the ECGs without waiting for a central assessment if an urgent decision is required to assure the patient's safety at the study center.

If a foreseeable abnormal ECG finding is observed (eg, QTcF > 480 ms), the study center should contact the Central ECG Reading Center to request immediate assessment (within 24 hours), and determine the action to be taken for the patient (dose increase or reduction of the study drug etc.) based on the central assessment results. In this case, triplicate ECGs should be obtained again within 2 hours after the ECG measurement in which the above abnormal finding has been detected, and the results should be submitted to the Central ECG Reading Center.

The analysis results of the Central ECG Reading Center will be regarded as the final ECG data. All QT-related events will be decided using QTcF.

Additional ECG may be performed if the investigators consider it necessary. In such a case, the time of the ECG should be recorded. Triplicate ECGs should be obtained at all

the measurement time points, and the QTcF determined as the average of the three recordings will be used as the representative ECG data.

Whether to measure the ECG or not, date and time of measurement, and investigators' assessment results will be recorded in the CRF.

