# Grade 2 (QTcF: 481 ms to 500 ms)

- Measure electrolyte levels (K+, Ca++, and Mg++) and supply the electrolytes to ensure recovery to the institutional reference ranges.
- Check concomitant drugs, and discontinue drugs that are known to prolong QTcF, as necessary.
- Reduce the dose of quizartinib by one level. It is not necessary to interrupt treatment.
- The dose may be increased to the dose before dose reduction if QTcF prolongation recovers to Grade 1 or less severe after treatment at the reduced dose for at least 28 days. However, whether prolongation of QT interval occurs or not should be confirmed carefully for the first cycle (28 days) after the dose increase.

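### From Cycle 2 Day 1 the dose-increase rule has no absolute QTcF limit, so a first Grade 2 QTcF (481 to 500 ms) can meet both the increase rule and the reduce-or-interrupt rule, and no sentence ranks them

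*Combined protocol and SAP*

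**What the plan says.** **Increase rule.** Section 5.2.4.3, for Day 1 of Cycle 2 or later, applies to patients not in CR, CRp or CRi after at least 13 consecutive days of dosing. If three requirements hold, the increase is worded as mandatory. They are no Grade 3 or worse related non-hematological toxicity, a "60 ms or shorter increase in QTcF interval from baseline", and no hypoplastic marrow. The Synopsis lists the same three. Table 5.2-2 moves 30 mg/day to 60 mg/day and 20 mg/day to 30 mg/day, with a cap of 30 mg/day for patients on a strong CYP3A4 inhibitor. By contrast, the Day 16 step of Cycle 1 has an absolute limit: every QTcF up to Day 15 must be 450 ms or shorter.

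**Reduce-or-interrupt rule.** Section 5.4 says that if any criterion in Sections 5.4.1 to 5.4.4 applies, "treatment with quizartinib will be interrupted or the dose of quizartinib will be reduced". For Grade 2 QTcF, which Section 9.10.2 defines as 481 to 500 ms:

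- at 30 or 60 mg/day (Table 5.4-2): "Reduce the dose by one level. It is not necessary to interrupt treatment";
- at 20 mg/day (Table 5.4-3): "Interrupt quizartinib treatment for a maximum of 14 days", with resumption at 20 mg/day after recovery to Grade 1 or less.

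**ECG handling.** Section 9.10.1 names QTcF above 480 ms as an example of an abnormal finding. It calls for repeat triplicate ECGs within 2 hours and a central read within 24 hours, and the site must then "determine the action to be taken for the patient (dose increase or reduction of the study drug etc.) based on the central assessment results".

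**The concern.** Both rules are worded as directives, and they point in opposite directions. The increase rule screens for the change in QTcF but not for its level. A patient who starts with a fairly long QTcF can therefore reach Grade 2 without breaching the 60 ms limit, and Grade 2 is below the Grade 3 toxicity bar.

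The gap also falls on patients one would not want to escalate by oversight. One main route to Cycle 2 Day 1 at the starting dose is to have had a QTcF above 450 ms by Day 15, and so to have missed the Day 16 increase. Those patients then meet a rule with no absolute limit, although Section 3.2.1 describes the QTc risk as dose-dependent. Section 15.5 allows no deviation except to remove an immediate hazard, so a site that follows either rule departs from the wording of the other.

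**Working it through.** The plan gives no figure to reproduce here. The check is where the two rules overlap, whether any sentence ranks them, and whether the number of patients can be estimated.

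**1. Where both rules apply**

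Inputs: Grade 2 is 481 to 500 ms (Section 9.10.2); the permitted rise is at most 60 ms (Section 5.2.4.3); screening QTcF must be below 450 ms (Section 4.2, criterion 12).

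Condition: QTcF − baseline ≤ 60, so baseline ≥ QTcF − 60. The lowest Grade 2 value gives 481 − 60 = 421 ms.

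| Baseline (ms) | Grade 2 values that still pass the 60 ms limit |
|---|---|
| 420 | none (481 − 420 = 61) |
| 421 | 481 only |
| 430 | 481 to 490 |
| 440 to 449 | 481 to 500 (all of Grade 2) |

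The upper end of 449 ms assumes that baseline stays under the screening limit. Section 11.1 defines baseline as the last value before the first dose, so it could be slightly higher.

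The patient must also be at 30 mg/day without a strong CYP3A4 inhibitor, or at 20 mg/day; must meet every other increase criterion; and must show Grade 2 for the first time at that visit. The following are outside the overlap: patients at 60 mg/day, patients held at the 30 mg/day cap by a strong inhibitor, related Grade 3 QTcF, and 30 mg/day patients already reduced for Grade 2, whom the 28-day rule in Section 5.4.5 governs.

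**2. Worked example at 30 mg/day, no strong inhibitor**

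- Baseline 430 ms.
- Day 15: 465 ms. Above 450, so no Day 16 increase; not Grade 2.
- Cycle 2 Day 1: 485 ms. Rise 485 − 430 = 55 ms, within the limit; Grade 2.
- Section 5.2.4.3 alone: 60 mg/day. Table 5.4-2: 20 mg/day. Ratio 60/20 = 3.

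At 20 mg/day with a strong inhibitor, the same clash is 30 mg/day against interruption.

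**3. Is there a ranking sentence?**

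- Section 5.2.4.1 refers to both rule sets without ordering them.
- Section 5.4.5 limits re-increase only once a reduction has been made.
- Section 9.10.1 names both directions and leaves the choice to the central result.
- Section 9.10.2 bars a later increase only after Grade 3.

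None says that Section 5.4 overrides Section 5.2.4.3.

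**4. Can the number of patients be estimated?**

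Table 1.2-1, 30 mg/day arm, N = 38: 5% is 2 patients and 47% is 18. So 2 had a maximum QTcF above 480 and up to 500 ms, and 2 were above 500 ms. The maximum rise was above 60 ms in 2, and the rise rows add up: 18 + 18 + 2 = 38.

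- Grade 2 maxima with a rise of 60 ms or less: at least 2 − 2 = 0, at most 2.
- Section 3.2.1 gives 3% (1 patient) for a rise above 60 ms, which would make the minimum 2 − 1 = 1. The rise rows would then total 18 + 18 + 1 = 37, so the table's figure is the more coherent one.

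Scaling to this trial, with 24 of 38 not in CRc after Cycle 1 (Section 3.2.2) and independence assumed: 41 × 2/38 × 24/38 = 1.4 patients, before the baseline, rise and timing conditions. The documents give no fraction for those conditions; any value from 0 to 1 gives 0 to 1.4. Even that range is unreliable. The exact 95% interval for 2/38 is 0.6% to 17.7%, and Section 3.2.2 says those 24 patients were raised to 60 mg, so the maxima can include 60 mg exposure.

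**The case against.** The strongest reply is that the protocol, read as a whole, already points one way. Section 5.2.4.1 first covers whether to increase, then says the dose will be reduced under each Section 5.4 criterion. Section 5.4 makes no exception for titration visits, and Section 9.10.2 repeats the Grade 2 reduction. Once the reduction is made, Section 5.4.5 allows return only to the previous dose, after at least 28 days and recovery. At 20 mg/day, Table 5.4-3 interrupts treatment and fixes the resumption dose, so there is no current dose to raise. Section 3.1 frames these visits narrowly: "Whether to increase or maintain the dose of quizartinib will be determined". All of this stands and makes reduction or interruption the natural reading. It remains an inference from several sections; none states it.

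A second reply also stands: the wording in Section 9.10.1 that names both directions is a general parenthesis covering whatever the central reader finds. A reader might infer from it that the protocol endorses escalating a confirmed Grade 2. It does not; it simply leaves the order of the two rules unsettled.

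A reader might also infer that the overlap has already been seen in the earlier Phase 2 study. At least 4 − 2 = 2 of the 4 patients above 480 ms in the 30 mg/day arm did rise by 60 ms or less, but by Table 1.2-1 both could be Grade 3. The Grade 2 count is 0 to 2, the values are whole-study maxima, and no baseline QTcF is given that would place anyone in the 421 to 449 ms range at a titration visit. Occurrence is not established. Section 3.2.2 also estimates that the QTc effect peaks on Day 15, so a first Grade 2 later at an unchanged dose is less likely.

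**Conclusion.** The point holds as a narrow conflict between two directives. For a non-responder at 30 mg/day without a strong CYP3A4 inhibitor, or at 20 mg/day, with a baseline of about 421 to 449 ms and a first Grade 2 QTcF at the decision visit, the increase rule and the reduce-or-interrupt rule are both met, and no sentence says which prevails.

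It is minor. Most sites would reduce or interrupt, and QTcF above 480 ms already triggers an urgent central read. The number affected is probably very small and cannot be estimated from the documents. What justifies acting is the consequence if the increase rule is followed alone: three times the dose that Table 5.4-2 requires, for a risk the protocol calls dose-dependent. Sample size, alpha, power and the CRc analysis are unaffected.

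The conclusion rests on the literal wording of both rules and on a baseline below the 450 ms screening limit. It does not rest on the earlier study's counts.

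**What to change.** Either of two changes is enough:

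- add to the Cycle 2 Day 1 or later criteria, in Section 5.2.4.3 and the Synopsis, a requirement that mean QTcF be 480 ms or shorter at the decision (no Grade 2 or more severe QTcF prolongation); or
- add one sentence stating that Section 5.4 takes precedence over Section 5.2.4.3.

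A stricter limit, such as the 450 ms used on Day 16, would be the sponsor's choice and is not needed to resolve the conflict.

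The cost is one criterion in two places, or one sentence, at the next amendment, with a note to sites. No new procedure is needed: triplicate ECGs are already scheduled on Day 1 of Cycle 2 and of later cycles (Section 6.2), and the repeat ECGs and 24-hour central read above 480 ms are already in Section 9.10.1. The downside is that a few non-responders with QTcF of 481 to 500 ms are not escalated at that visit; Section 5.4.1 already directs reduction or interruption for them.

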## 5.2.5 Storage

The study drug manager will store and manage the study drug at 25°C or lower without freezing.

#### 5.2.6 Drug Accountability

After receiving the delivered study drug, the study drug manager or designee will check the quantity and condition of the study drug and confirm the appropriateness of the labeling as well as the expiry date of the study drugs etc. In addition, the investigator or designee shall contact the sponsor as soon as possible if there is a problem with the study drug.

The study drug will be managed using the Drug Accountability Record. The Accountability Record must be updated, and should contain such information as the date of receipt of the study drug, the quantity of the received study drug, patients supplied with the study drug (identification number, or if applicable, supply number), date of supply of the study drug, quantity supplied and residual quantity, and the signed initials and seal of the person who supplied the study drug. At the end of the study, the investigator or designee must prepare the final version of the study drug management-related record, and submit it to the sponsor.

Other procedures related to study drug management and collection will be performed in accordance with the "Study Drug Management Procedures."

## 5.3 Control Treatment

Not applicable

## 5.4 Dose Interruptions and Reductions

If any of the criteria in Section 5.4.1 to Section 5.4.4 apply, treatment with quizartinib will be interrupted or the dose of quizartinib will be reduced. The dose of quizartinib will be reduced by one level at a time according to Table 5.4-1. If quizartinib is administered at a dose of 20 mg/day, a further dose reduction is not allowed.

Table 5.4-1 Method of Dose Reduction of Quizartinib

Dose	One level Reduced Dose
60 mg/day	30 mg/day
30 mg/day	20 mg/day
20 mg/day	No dose reduction

## **5.4.1 QTcF Prolongation**

In case of QTcF prolongation, the dose will be reduced in the following manner.

Table 5.4-2 Criteria for Dose Interruption and Reduction When QTcF Prolongation Occurs during Treatment with Quizartinib at 30 mg/day or 60 mg/day

CTCAE Grade	Method of Dose Reduction		
Grade 2	
 
Reduce the dose by one level. It is not necessary to interrupt treatment.
 
The dose may be increased to the dose before dose reduction if QTcF prolongation recovers to Grade 1 or less severe after treatment at the reduced dose for at least 28 days.
 
		
Grade 3	
 
Interrupt quizartinib treatment for a maximum of 14 days.
 
Resume quizartinib treatment at a one level reduced dose, relative to the dose immediately before the interruption, if the increase in QTcF interval from baseline is 30 ms or shorter or the QTcF interval recovers to 450 ms or shorter within 14 days after the onset.
 
Do not increase the dose after resumption of quizartinib treatment.
 
		
Grade 4	Discontinue quizartinib treatment.		

For the treatment of QTcF prolongation, "9.10.2 Measures Taken in Case of QTcF Prolongation" should be followed.

Table 5.4-3 Criteria for Dose Interruption and Reduction When QTcF Prolongation Occurs during Treatment with Quizartinib at 20 mg/day

CTCAE Grade	Method of Dose Reduction	
Grade 2	
 
Interrupt quizartinib treatment for a maximum of 14 days.
 
Resume quizartinib treatment at a dose of 20 mg/day if QTcF prolongation recovers to Grade 1 or less severe.
 
	
Grade 3	
 
[If strong CYP3A4 inhibitors are concomitantly used]
 
Interrupt quizartinib treatment for a maximum of 14 days.
 
Resume quizartinib treatment at a dose of 20 mg/day if the increase in QTcF interval from baseline is 30 ms or shorter or the QTcF interval recovers to 450 ms or shorter within 14 days after the onset, and the concomitant use of strong CYP3A4 inhibitors is discontinued.
 
Do not increase the dose after resumption of quizartinib treatment.
 
[If strong CYP3A4 inhibitors are not concomitantly used]
 
Discontinue quizartinib treatment.
 
	
Grade 4	Discontinue quizartinib treatment.	

For the treatment of QTcF prolongation, "9.10.2 Measures Taken in Case of QTcF Prolongation" should be followed.

### 5.4.2 Non-hematological Toxicity

If a quizartinib-related Grade 3 or more severe non-hematological toxicity does not improve to Grade 2 or less severe, and it persists for at least 48 hours, treatment with quizartinib should be interrupted for a maximum of 14 days when quizartinib has been administered at a dose of 30 mg/day or 60 mg/day. If the toxicity recovers to Grade 1 or less severe within 14 days after the onset, treatment with quizartinib may be resumed at a reduced dose. When quizartinib is administered at a dose of 20 mg/day, treatment with quizartinib should be discontinued.

#### **5.4.3** Bone Marrow Depression

If all of the following criteria apply in patients achieving CRp or CRi, dose reduction should be considered in the opinion of the investigators. If an improvement in bone marrow depression is not observed even after dose reduction, interruption of treatment for a maximum of 14 days should be considered (also when quizartinib is administered at a dose of 20 mg/day in patients meeting all of the following criteria, interruption of treatment should be considered).

- Completion of 1 or more cycles of treatment with quizartinib
- Platelet count of less than 100 000/mm^3 and neutrophil count of 1000/mm^3 or less
- Less than 5% blasts in the bone marrow
- Absence of extramedullary lesions

If an improvement in bone marrow depression is observed within 14 days after interruption of treatment, treatment with quizartinib may be resumed at the dose before interruption of treatment. If the dose before interruption of treatment is 20 mg/day, the treatment may be resumed at 20 mg/day.

# 5.4.4 If Concomitant Use of Strong CYP3A4 Inhibitors Is Started during the Study Period

If concomitant use of strong CYP3A4 inhibitors is started during the study period, the dose of quizartinib will be reduced by one level. If concomitant use of strong CYP3A4 inhibitors is discontinued, quizartinib may be administered at the dose used before dose reduction after a 7-day washout.

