Increased QT/QTc interval to longer than 500 ms and an increase of longer than 60 ms in QT/QTc interval from baseline are important changes to decide whether to conduct a clinical study or not. According to the results of Study 2689-CL-2004, the incidence of increased QTc interval to longer than 500 ms was as low as 5% or less in the 30 mg and 60 mg groups, and the incidence of a longer than 60 ms increase in QTc interval from baseline was lower in the 30 mg and 60 mg groups than in the 90 mg or higher dose groups. Based on these data, it was considered that quizartinib is tolerated at doses of 30 mg and 60 mg, and the initial dose of 30 mg was chosen in this study. The rationale for setting 20 mg/day as the initial dose of quizartinib for patients concomitantly using strong CYP inhibitors is shown below.

In a drug-drug interaction study in healthy adult subjects, ketoconazole (strong CYP3A4 inhibitor) or fluconazole (moderate CYP3A4 inhibitor) was administered as multiple doses, followed by quizartinib as a single dose; concomitant treatment with ketoconazole or fluconazole resulted in 1.17-fold or 1.11-fold Cmax, respectively, and 1.94-fold or 1.20-fold AUCinf, respectively, compared with quizartinib monotherapy. Based on this result, it was estimated that the steady-state plasma quizartinib concentration following administration of multiple-dose quizartinib concomitantly with ketoconazole or fluconazole would increase by 1.86-fold or 1.21-fold, respectively, for Cmax and by 1.96-fold or 1.21-fold, respectively, for AUC0.24, compared with quizartinib monotherapy. This result indicates that exposure to quizartinib nearly doubles when quizartinib is concomitantly used with strong CYP3A4 inhibitors, and it was therefore considered appropriate to administer quizartinib at a dose of 20 mg/day, which is about half the dose, in the presence of strong CYP inhibitors. Meanwhile, exposure to quizartinib concomitantly used with moderate CYP3A4 inhibitors is limited, and it was therefore considered unnecessary to reduce the dose of quizartinib in the presence of moderate CYP3A4 inhibitors. The initial dose of quizartinib in Study AC220-007 was set at 30 mg/day (20 mg/day in the presence of strong CYP3A4 inhibitors) for the same reason.

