In addition, when the relationship between drug concentrations and QTc interval was evaluated using the data from Study 2689-CL-2004, a linear relationship between prolongation of QTc interval and plasma AC220 concentrations was found. The half-life of AC220 was approximately 3 days, and quizartinib exposure reached a steady state on Day 15 of Cycle 1 in both the 30 mg and 60 mg groups. Therefore, prolongation of QTc interval caused by AC220 was estimated to reach a peak on Day 15 of Cycle 1. Data from Study 2689-CL-2004 did not show any significant correlation between plasma AC886 concentrations and prolongation of QTc interval. In view of these data, it was considered possible to increase the dose of quizartinib from 30 mg to 60 mg on Day 16 of Cycle 1 or later based on the assessment on Day 15 of Cycle 1, when the plasma quizartinib concentration reaches a steady state, in accordance with "5.2.4.3 Criteria for Dose Increase of the Study Drug."

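### Section 5.4.4 does not say what applies when a strong CYP3A4 inhibitor is started at 20 mg/day; staying at 20 can give a patient reduced from 30 mg/day for QTcF prolongation more exposure than at the event

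*Combined protocol and SAP*

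**What the plan says.** Section 5.4.4 covers a strong CYP3A4 inhibitor started on study: "If concomitant use of strong CYP3A4 inhibitors is started during the study period, the dose of quizartinib will be reduced by one level". It makes no exception for any dose. It adds only that the previous dose may be restored once the inhibitor has been stopped and a 7-day washout has passed. Section 5.4.5 repeats that provision.

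Section 5.4 opens with a rule over all four subsections: where one of them applies, the drug is either paused or lowered, one level at a time under Table 5.4-1. The table steps from 60 to 30 and from 30 to 20 mg/day, and its last row reads "20 mg/day No dose reduction". The text agrees: "If quizartinib is administered at a dose of 20 mg/day, a further dose reduction is not allowed".

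The other three subsections each provide for a patient at 20 mg/day. Table 5.4-3 gives the QTcF actions, Section 5.4.2 ends treatment, and Section 5.4.3 has interruption considered. Starting a strong inhibitor at 20 mg/day is not among the discontinuation criteria of Section 5.7.1.

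On exposure, Section 3.2.1 says that "exposure to quizartinib nearly doubles when quizartinib is concomitantly used with strong CYP3A4 inhibitors". On its consequence, Section 3.2.2 reports that "a linear relationship between prolongation of QTc interval and plasma AC220 concentrations was found".

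**The concern.** A patient can reach 20 mg/day without an inhibitor because of the drug's effect on QTcF. Under Table 5.4-2, Grade 2 prolongation at 30 mg/day leads to 20 mg/day without interruption. Grade 3 leads to interruption and then resumption at 20 mg/day. If that patient later needs a strong inhibitor (Appendix 4 lists itraconazole and voriconazole among them), Section 5.4.4 calls for a step that Table 5.4-1 does not contain. No text says whether to continue, interrupt or stop.

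If the patient simply stays at 20 mg/day, the interaction nearly doubles exposure in someone whose dose was lowered because of QTcF. The stake is patient safety and uniform handling across sites. No consequence for the primary endpoint or the two-stage decision rule is shown.

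**Working it through.** **Inputs**
- Fold increase in quizartinib with ketoconazole, Section 3.2.1: single-dose Cmax 1.17 and AUCinf 1.94; predicted steady-state Cmax 1.86 and AUC over 24 hours 1.96. Section 1.2.1.2.5 rounds the AUCinf effect to about 2-fold.
- Dose levels 60, 30 and 20 mg/day, Table 5.4-1.
- Dose proportionality, Section 1.2.1.2.5: reported for 30 to 90 mg. Extending it to 20 mg is an assumption.

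**The protocol's own figure.** Under linear kinetics, steady-state AUC over a dosing interval equals single-dose AUCinf, so the expected ratio is 1.94. The stated 1.96 differs by 1.96/1.94 − 1 = 1.0%, so it is reproduced. The steady-state Cmax ratio of 1.86 cannot be rebuilt without concentration profiles and is taken as stated.

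**Exposure at 20 mg/day with a strong inhibitor.** Equivalent dose without an inhibitor = 20 × fold increase; the comparison is with 30 mg/day without an inhibitor.

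| Measure | Fold | Equivalent, mg/day | Ratio to 30 mg/day |
|---|---|---|---|
| Cmax, steady state | 1.86 | 37.2 | 1.24 |
| AUCinf | 1.94 | 38.8 | 1.29 |
| AUC over 24 h, steady state | 1.96 | 39.2 | 1.31 |
| Rounded AUCinf | 2.0 | 40.0 | 1.33 |

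The break-even fold is 30/20 = 1.5, and all four figures exceed it. The single-dose Cmax ratio does not (20 × 1.17 = 23.4), but it does not describe daily dosing of a drug with a half-life of about 3 days and roughly 4-fold accumulation.

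**Where the excess does not arise**
- Event at 60 mg/day: 39.2/60 = 0.65, so exposure is lower than at the event.
- Event at 30 mg/day already on an inhibitor: exposure then was 30 × 1.96 = 58.8, above 39.2.
- Step from 60 to 30 mg/day when an inhibitor starts: 58.8/60 = 0.98, close to neutral. The one-level rule works there.

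**Comparison with Table 5.4-3.** After Grade 3 prolongation at 20 mg/day with a strong inhibitor, that table permits a return to 20 mg/day only if QTcF has recovered and the inhibitor has been stopped. A patient with Grade 3 at 30 mg/day alone, now at 20 mg/day, can arrive at 20 mg/day with an inhibitor through the silence of Section 5.4.4. The two histories differ, but the same combination is barred after one and unaddressed after the other.

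**Rough frequency.** Table 1.2-1 shows 5% Grade 2 and 5% Grade 3 by maximum QTcF in the 30 mg group of the earlier study. If these applied to 41 patients, 41 × 0.10 = 4.1 would have such an event before any inhibitor is considered. This is indicative only: Section 3.2.2 says 24 of the 38 patients in that group went up to 60 mg, and the table does not separate events by dose at onset.

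**The case against.** The strongest reply is structural. Section 5.4 governs Section 5.4.4, and a level means a row of Table 5.4-1. At 20 mg/day that row allows no reduction, so the combined instruction is to stay at 20. This is a fair reading. A reader might infer that a site cannot comply with both rules; the documents do not force that conclusion. But this reading is the one that produces the exposure calculated above, and it still leaves open whether to continue, interrupt or stop.

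Second, 20 mg/day with a strong inhibitor is the accepted starting regimen (Section 5.2.4.1), and 30 mg/day is the cap with an inhibitor (Section 5.2.4.3). That stands: about 39 mg/day equivalent is not in itself outside the plan. However, patients start that regimen with screening QTcF below 450 ms, and the Day 16 increase requires every QTcF to be 450 ms or shorter. The gap concerns patients who have already been reduced for QTcF.

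Third, there are safeguards. Section 5.6.2.2 tells sites to avoid strong inhibitors, although it does not ban them. Section 5.6.2.1 prohibits QT-prolonging drugs unless medically unavoidable. Section 9.10.2 asks for further ECGs after a QTcF-related reduction, and Section 5.7.1 lets the investigator stop treatment. These narrow the problem without closing it. The ECG timing in Section 9.10.2 is left open, the weekly ECGs of Section 5.2.4.3 follow a dose increase rather than the start of an inhibitor, and Table 5.4-3 acts only once prolongation recurs.

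Three stronger inferences are tempting and are not supported:
- That the bar after Grade 3 is breached. Table 5.4-2 says "Do not increase the dose after resumption of quizartinib treatment"; it restricts dose, and an interaction raises exposure without changing the dose.
- That the torsades de pointes case shows the risk at this exposure. It occurred at 90 mg/day with a strong inhibitor (Section 1.2.1.2.2), which on the same multiplier is 90 × 1.96 = 176.4 mg/day equivalent.
- That the rationale in Section 3.2.1 for "a dose of 20 mg/day, which is about half the dose, in the presence of strong CYP inhibitors" is a dosing error. The ratio 20/30 is two thirds, so the wording is loose, but it changes no instruction.

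**Conclusion.** The point holds in a limited form. Sections 5.4.4 and 5.4.5 lack the provision for 20 mg/day that the other three rules have. Under the most natural reading, one group of patients ends up above the exposure at which QTcF prolongation occurred. The excess is 24% to 33%, or 37.2 to 40.0 against 30 mg/day.

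It applies only to an event at 30 mg/day without an inhibitor, followed by reduction to 20 mg/day and then a newly started strong inhibitor. A reader might extend it to every patient reduced for QTcF; the figures for an event at 60 mg/day, or at 30 mg/day on an inhibitor, show otherwise. It assumes proportionality down to 20 mg and a ketoconazole-like effect from the inhibitor used.

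This should be fixed because it concerns safety and costs little. It does not threaten the trial's analysis, and the number of patients affected is likely to be small.

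**What to change.** Reconcile Sections 5.4, 5.4.4 and 5.4.5 and Tables 5.4-1 and 5.4-3 so that they give one consistent instruction for a patient already at 20 mg/day when a strong CYP3A4 inhibitor is started. The instruction should expressly cover a patient who is at 20 mg/day because of QTcF prolongation. What it should require is a clinical decision for the sponsor.

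The cost is a protocol wording amendment with the usual ethics review. Sample size, stopping criteria and planned analyses are unaffected.
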